## 4.5.2.2 Overview of Adverse Events

To provide an overview of patient safety results, an AE profile summary table will be presented. For each randomized group, this will show the following:

Total number of patients (and percentage) with at least one AE

Total number of AEs

Total number of deaths (and percentage)

Total number of patients (and percentage) with at least one of:

- AE with fatal outcome
- Serious AE (SAE)
- Serious infection (defined using AEs falling into the MedDRA "Infections and Infestations" SOC and "serious" responses to the question "Is the event nonserious or serious?" from the "Adverse Event/IRR/MS Relapse" eCRF page)

- SAE leading to withdrawal from ocrelizumab treatment (withdrawal from ocrelizumab treatment defined as "drug withdrawn" in response to the SAE, taken from the "Adverse Event/IRR/MS Relapse" eCRF page)
- SAE leading to ocrelizumab dose modification/interruption (modification/interruption defined as "dose delayed", "dose reduced" or "drug temporarily interrupted" in response to the SAE, taken from the "Adverse Event/IRR/MS Relapse" eCRF page)
- AE leading to withdrawal from ocrelizumab treatment (withdrawal from ocrelizumab treatment defined as "drug withdrawn" in response to the AE, taken from the "Adverse Event/IRR/MS Relapse" eCRF page)
- AE leading to ocrelizumab dose modification/interruption (modification/interruption defined as "dose delayed", "dose reduced" or "drug temporarily interrupted" in response to the AE, taken from the "Adverse Event/IRR/MS Relapse" eCRF page)
- IRRs leading to withdrawal from ocrelizumab treatment at the 1st Randomized Dose
- Malignancies (defined using AEs falling into the Standard MedDRA Query "Malignant tumours (narrow)" from the "Adverse Event/IRR/MS Relapse" eCRF page)
- Infections (defined using AEs falling into the MedDRA "Infections and Infestations" SOC from the "Adverse Event/IRR/MS Relapse" eCRF page)

The AE profile summary described above will be repeated per 100 patient-years (100PY) exposure, in order to adjust for any differences between randomized groups in the duration of observation period. Estimates of incidence rates per 100PY will be provided, along with associated 95% CIs. For further details, please refer to the "Common Adverse Events" section later in this document.

## 4.5.2.3 Common Adverse Events

AEs will be defined as all AEs including IRRs and serious MS relapses, but excluding non-serious MS relapses. Therefore, those AEs recorded on the "Adverse event/IRR/MS relapse" eCRF page will be included.

AEs reported from randomization onwards at all randomized doses will be included in summary tables. These summary tables will show all AEs combined, and will not show any separate summaries by Randomized Dose nor Dose.

All AEs with an onset date after the date of randomization will be included, even if the onset is after the patient discontinues randomized treatment. AEs will be flagged by substudy period based on time of onset, as described at the end of Section 2 (periods are "Randomized Period", "Post Substudy, On Treatment" and "Post Substudy, Off Treatment"). For each AE recorded, the term entered by the investigator describing the event (the "reported term") will be assigned a standardized term (the "preferred term" (PT)) based on the Medical Dictionary for Regulatory Activities (MedDRA) World Health Organization (WHO) dictionary of terms. All analyses of AE data will be performed using the PTs unless otherwise specified. All AEs will be mapped to PTs and system organ classes (SOCs).

Summaries of AEs will be generated summarizing the incidence of treatment-emergent AEs only. These are defined as either: a) AEs with an observed or imputed date of AE onset which is on or after the date of 1st Randomized Dose or b) AEs with an observed or imputed date of AE onset which is before the date of 1st Randomized Dose and which worsens in intensity. An AE with a completely missing non-imputed start date will be assumed to be treatment emergent unless the AE event has a complete non-imputed end date which is prior to the date of the 1st Randomized Dose. In this substudy, the term "treatment-emergent" will always be used to mean "randomization-emergent" (it does not refer to the first dose of ocrelizumab treatment in the main study).

For each randomized group, the incidence count for each AE PT will be defined as the number of patients reporting at least one treatment-emergent occurrence of the event. The incidence rate will be calculated as the incidence count divided by the total number of patients in the population. In some summaries, AEs will also be evaluated by exposure time (incidence rate per 100 patient-years (100PY) exposure), in order to adjust for any differences between randomized groups in the duration of observation period. Estimates of incidence rates per 100PY will be provided, along with associated 95% CIs calculated using an exact method based on the Poisson distribution. Each table will also present the overall number of patients experiencing at least one AE and the total number of AEs reported. Multiple occurrences of the same AE in the same patient will be counted only once at the greatest intensity/highest grade for this PT. For AEs leading to death, the most extreme intensity will be overwritten by Grade 5 (death).

SAEs are defined as all serious AEs, including serious MS relapses and serious IRRs.

The number and percentage of patients experiencing adverse events will be presented by SOC and PT. This summary will be repeated per 100PY to account for the duration of patient exposure.

The most frequent AEs ( $\geq$ 5% in either randomized group) will be presented by PT.

The number and percentage of patients experiencing AEs suspected to be caused by ocrelizumab will be presented by SOC and PT.

All AEs occurring post-randomization will be listed.

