## 4.5.1 Exposure to Study Medication

Within the substudy, in both randomized groups ocrelizumab is given as single infusions of 600mg at 24-week intervals. The only difference between the randomized groups is the duration of the infusion.

Patients will be considered to have received a dose of treatment if at least part of that infusion was given. If a dose is completely missed instead of delayed, the next dose number will be based on the number of previous doses received.

For each patient, the length of exposure to randomized treatment is from the date on which the patient first received randomized treatment (Substudy Day 1) until the last known alive date or CCOD, whichever is earlier. For patients who withdrew early from randomized treatment, the exposure is until the last known alive date (i.e., duration of exposure is equivalent to duration of observation period, and these terms are used interchangeably in this SAP). To summarize, the duration of exposure for a patient will be calculated as:

(Date of last contact\* – date of 1st Randomized Dose) + 1

\* Earlier of 1) date of CCOD 2) last known alive date

The following aspects of exposure to ocrelizumab will be summarized by randomized group:

- Treatment duration (weeks): frequency counts (number of patients and percentage) for 0-23 weeks, 24-47 weeks and 48-71 weeks will be presented
- Number of doses received: frequency counts (number of patients and percentage) and summary statistics (mean, SD and median) will be presented
- Total cumulative dose (derived to mg): summary statistics (mean, SD, median, lower and upper quartiles, minimum and maximum) will be presented

- Ocrelizumab infusion duration (minutes): summary statistics (mean, SD, median, lower and upper quartiles, minimum and maximum) will be presented by Randomized Dose and overall (all randomized doses).
- The number and percentage of infused patients with < 80% and ≥ 80% of the planned infusion volume will be presented, along with the number and percentage of infused patients who were pre-treated with methylprednisolone (or equivalent) only, with antihistamine only and with both methylprednisolone (or equivalent) and antihistamine. These summaries will be presented by Randomized Dose and then by Dose within Randomized Dose (and overall within Randomized Dose i.e. across all Doses).

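### The AE rates per 100 patient-years count each affected patient once but keep adding that patient's time after the event, so rates for common events come out too low

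*SAP*

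**What the plan says.** All of the following is in the shorter-infusion SAP.

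- **Numerator.** Section 4.5.2.3 states that "the incidence count for each AE PT will be defined as the number of patients reporting at least one treatment-emergent occurrence of the event". It adds: "Multiple occurrences of the same AE in the same patient will be counted only once at the greatest intensity/highest grade for this PT". This is the only count the SAP defines.
- **Rate and interval.** The same paragraph introduces an "incidence rate per 100 patient-years (100PY) exposure", to allow for differences between groups in length of observation, with "associated 95% CIs calculated using an exact method based on the Poisson distribution".
- **Patient-time.** Section 4.5.1 runs each patient's exposure "until the last known alive date or CCOD, whichever is earlier". Patients who leave randomized treatment early keep accruing time, and the section states that "duration of exposure is equivalent to duration of observation period, and these terms are used interchangeably in this SAP".
- **Tables affected.** These are the tables by system organ class and preferred term (4.5.2.3), the serious AE table (4.5.2.6) and the overview (4.5.2.2): "The AE profile summary described above will be repeated per 100 patient-years (100PY) exposure". Most overview rows count patients with at least one event; one row is the total number of AEs.

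No section stops patient-time at a first event or defines a different numerator for the per-100PY version.

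**The concern.** Once a patient has had a given event, that patient can add nothing more to the count but goes on adding time. The ratio is then the proportion affected divided by the length of follow-up, which is not an incidence rate. For an event at a constant rate it drifts down as follow-up grows. For a rare event the difference is negligible; for a common one it is not.

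These tables exist to correct for unequal observation time, and for common terms they do so only in part. The shortfall occurs in both arms, but it does not cancel in a ratio: it pulls the ratio for common terms towards 1, which is an unhelpful direction in a safety comparison. Frequent terms do occur here. Infusion-related reactions (IRRs) count as AEs in Section 4.5.2.3, and Protocol Section 1.2 reports them in 23.1% and 24.6% of the two groups at the first randomized infusion.

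**Working it through.** The SAP gives no per-100PY figure, so there is nothing to reproduce. The check compares the rate as written with a first-event rate.

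**Inputs**
- Proportions affected over 96 weeks on ocrelizumab, pooled relapsing MS trials (Protocol Section 1.2): any AE 83.3%, infections 58.4%, serious AEs 6.9%.
- Follow-up: the interim cut-off is 27 September 2019 (SAP Section 1). The first already-enrolled patient was randomized on 1 November 2018 and the first newly enrolled patient on 22 March 2019 (SAP Section 2). The longest possible interim follow-up is therefore 330 days (0.9 years) and 189 days respectively. The exposure bands in SAP Section 4.5.1 end at 71 weeks. The documents give no mean follow-up, so a range is used.
- Assumptions: constant hazard, and the same follow-up T for every patient.

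**Formulas**
- First-event rate: λ = −ln(1 − p)/T, with T = 96/52.18 = 1.84 years.
  - Infections: −ln(0.416)/1.84 = 0.477, or 47.7 per 100PY.
  - Any AE: −ln(0.167)/1.84 = 0.973, or 97.3 per 100PY.
  - Serious AEs: −ln(0.931)/1.84 = 0.0389, or 3.89 per 100PY.
- Rate as the SAP reads: (1 − e^(−λT))/T. For infections at 0.5 years: (1 − e^(−0.238))/0.5 = 0.212/0.5, or 42.4 per 100PY, which is 11% below 47.7.

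**Rate as written, per 100PY (shortfall against the first-event rate)**

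| Follow-up | Infections (47.7) | Any AE (97.3) | Serious AEs (3.89) |
|---|---|---|---|
| 0.25 years | 44.9 (6%) | 86.4 (11%) | 3.87 (0.5%) |
| 0.5 years | 42.4 (11%) | 77.0 (21%) | 3.85 (1.0%) |
| 0.9 years | 38.8 (19%) | 64.8 (33%) | 3.82 (1.7%) |
| 71 weeks (1.36 years) | 35.1 (26%) | 53.9 (45%) | 3.79 (2.6%) |

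**Dependence on follow-up.** At a true rate of 100 per 100PY, the formula gives 78.7 at 0.5 years and 65.9 at 0.9 years.

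**Effect on a ratio.** True rates of 130 and 100 per 100PY, both followed for 0.9 years, give (1 − e^(−1.17))/0.9 = 76.6 and (1 − e^(−0.9))/0.9 = 65.9. The ratio appears as 1.16 instead of 1.30.

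**Interval.** A count of affected patients is binomial, with variance/mean = 1 − p, whereas a Poisson count has 1. Exact Poisson limits are therefore too wide for the count. In 20,000 simulated trials per setting with 289 patients (the shorter-infusion group size in Protocol Section 1.2), they covered their own target p/T about 98% of the time at p = 25% and 99.6% at p = 50%. Because they are centred too low, they covered the first-event rate about 82% of the time at p = 25% and never at p = 50%. With patient-time stopped at the first event, the same exact interval covered the first-event rate in 95 to 96% of trials for p from 5% to 80%.

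**The case against.** **The formula is never written out.** The reading joins two sections. Exact Poisson limits over full exposure are the natural pair for event counts, the overview includes a total-AE row, and the protocol itself reports serious infections as an event rate. The sponsor may have meant all events over total exposure. It is fair to call the fault inferred. But the only numerator defined is patients, and the tables to be repeated per 100PY are patient tables. If events were intended, the defined count is wrong and the text still needs changing.

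**The consequence is limited.** This stands. The substudy is descriptive, randomization is 1:1 and stratified so follow-up should be similar by arm, and percentages and AE listings accompany the rates. Deaths are untouched because follow-up ends at the event, and malignancies and serious infections barely move.

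**Three stronger readings that a reader might infer are not supported.**
- *Rates are a third to a half too low.* Over a full 96 weeks the formulas give 31.7 against 47.7 for infections (33% low) and 45.3 against 97.3 for any AE (53% low). The interim data cannot reach 96 weeks, and the exposure bands stop at 71.
- *The Poisson intervals are too narrow.* For patient counts the opposite is true. Narrowness arises only for event counts, where events cluster within patients. The earlier trials' 1,224 infections with 58.4% affected, and a group size of 727 to 889 (back-calculated from 4 patients being a rounded 0.5%), fit a negative binomial. At 0.5 years that implies intervals 1.17 to 1.27 times as wide as Poisson.
- *Stopping time at the first event makes interim and final IRR rates comparable.* It does not, because IRRs cluster at infusions. Take 71 of 289 at the first randomized dose (Protocol Section 1.2), events at time zero and no later first IRRs. The SAP rate is 49.1 per 100PY at 0.5 years and 24.6 at 1 year; with time stopped at the event it is 65.1 and 32.6. Both halve.

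**Conclusion.** The point holds in a limited form. As written, the per-100PY rates pair a first-event count with time that continues after the event. The mismatch matters for common terms and is trivial for rare ones: over 0.25 to 0.9 years about 6 to 19% for infections, 11 to 33% for any AE, and under 2% for serious AEs. The sizes are illustrative. They rest on a constant hazard, equal follow-up for all patients, and proportions borrowed from trials that included the first dose, which the randomized period does not. The conclusion also rests on reading Sections 4.5.1 and 4.5.2.3 together, since no formula is given. Nothing here touches the primary endpoint, which is a proportion at the first randomized infusion. A clarification with a small correction is warranted; the substudy's main conclusion is not in question.

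**What to change.** Amend SAP Section 4.5.2.3, and refer to it from 4.5.1, 4.5.2.2 and 4.5.2.6:

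- **Patient-count rows.** End each patient's time at risk at the first occurrence of that event, or at last known alive date or cut-off if there is none. Keep the exact Poisson interval.
- **Event-count rows, such as total number of AEs.** Use all events over total exposure, with a negative binomial or patient-level robust interval.
- **Labels.** State numerator and denominator on every row.
- **IRRs.** Rely on the proportions by randomized dose that Section 4.5.2.1 already plans, rather than on a rate over calendar time.

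The cost is a few lines of SAP text and some additional programming, because time at risk becomes specific to each term. Stated rates for common events will look less favourable. Where tables have already been produced, re-run them or add a footnote giving the definition used.

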# 4.5.2.4 Adverse Events by Intensity

The number and percentage of patients experiencing AEs will be presented by most extreme intensity by SOC and PT. This summary will be repeated showing only AEs with maximum intensity of Grade 3, 4 or 5.

## 4.5.2.5 Deaths

All patient deaths occurring post-randomization will be listed.

## 4.5.2.6 Serious Adverse Events

The number and percentage of patients experiencing an SAE will be summarized by SOC and PT. This summary will be repeated per 100PY to account for the duration of patient exposure.

The number and percentage of patients experiencing SAEs suspected to be caused by ocrelizumab will be presented by SOC and PT.

The number and percentage of patients experiencing SAEs will be presented by most extreme intensity by SOC and PT.

All SAEs occurring post-randomization will be listed.

## 4.5.2.7 Adverse Events Which Led to Early Discontinuation from Ocrelizumab Treatment

The number of patients experiencing an AE which led to early discontinuation from ocrelizumab treatment will be summarized by SOC and PT.

All AEs which led to early discontinuation from ocrelizumab treatment will be listed.

## 4.5.2.8 Adverse Events Which Led to Modification or Interruption of Ocrelizumab Treatment

The number of patients experiencing an AE which led to modification or interruption of ocrelizumab treatment will be summarized by SOC and PT.

# 4.5.2.9 Pregnancies

Information on pregnancy tests and pregnancy outcomes post-randomization will be listed.

## 4.5.3 Laboratory Data

## 4.5.3.1 Hematology and Biochemistry

All available laboratory assessments (hematology and biochemistry separately) will be summarized in the IA (N=400 approximately) and in the analysis of all randomized patients (N=650 to 700 approximately).

To summarize laboratory data, all assessments, both scheduled and unscheduled, will be included. Visit windows will be applied as follows:

- Randomization: most recent available assessment prior to substudy randomization (Substudy Day 1)
- 24 weeks after 1st Randomized Dose: include all assessments after substudy randomization (Substudy Day 2) up to 36 weeks after 1st Randomized Dose (Substudy Day 253)
- 48 weeks after 1st Randomized Dose: include all assessments from the day after 36 weeks after 1st Randomized Dose (Substudy Day 254) to 60 weeks after 1st Randomized Dose (Substudy Day 421)
- 72 weeks after 1st Randomized Dose: include all assessments from the day after 60 weeks after 1st Randomized Dose (Substudy Day 422) to 84 weeks after 1st Randomized Dose (Substudy Day 589)
- 96, 120, 144 etc weeks after 1st Randomized Dose: continue to define windows in the same way as described above

If multiple values of the same laboratory parameter occur within the same time window, the worst value for that parameter will be presented in the summary table.

Absolute value and change from randomization values at each visit (24 weeks after 1st Randomized Dose, 48 weeks after 1st Randomized Dose etc.) will be summarized (mean, SD, median, minimum and maximum).

A summary of the number and percentage of patients with single and replicated laboratory abnormalities will presented for each laboratory parameter.

## 4.5.3.2 CD4, CD8 and CD19

All available CD4, CD8 and CD19 assessments will be summarized in the IA (N=400 approximately) and in the analysis of all randomized patients (N=650 to 700 approximately).

Visit windows will be applied to CD4, CD8 and CD19 assessments in the same way as described above for hematology and biochemistry.

Summary statistics will be presented for CD19 values, separately for patients experiencing IRRs during/post-infusion versus patients not experiencing IRRs. Additionally, box plots of CD19 values versus IRR maximum intensity will be presented (by Randomized Dose). These are considered exploratory summaries.

Absolute value and change from randomization values at each visit (24 weeks after 1st Randomized Dose, 48 weeks after 1st Randomized Dose etc.) will be summarized (mean, SD, median, minimum and maximum).

# 4.5.4 Vital Signs

Vital signs parameters are systolic blood pressure, diastolic blood pressure and pulse rate (body temperature is not included -- measurement of body temperature after the main study screening visit was required in earlier versions of the protocol, but in later versions this was only required at screening, but at any time sites could record body temperature for specific reasons e.g. temperature increase).

Vital signs parameters prior to start of each ocrelizumab infusion (baseline) and at 15, 30, 45 minutes, 1, 1.5, 2, 2.5, 3, 3.5, 4, 4.5 and 5 hours post start of ocrelizumab infusion and 1 hour post end of ocrelizumab/saline infusion will be summarized (mean, SD, median, minimum and maximum). The change from baseline will also be summarized (mean, SD, median, minimum and maximum). Additionally, box plots of each vital signs parameter during the time of the infusion will be presented (by Randomized Dose).

Vital signs abnormalities are defined as follows:

- Systolic blood pressure <90mmHg or >140mmHg
- Diastolic blood pressure <50mmHg or >90mmHg
- Pulse rate <60pm or >100bpm

The number and percentage of patients with any vital signs abnormalities and with each abnormality described above will be presented, for all patients, for patients experiencing IRRs during/post-infusion and for patients not experiencing IRRs. These summaries will be presented by Randomized Dose and then by Dose within Randomized Dose (and overall within Randomized Dose i.e., across all Doses).

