• On infusion visits, three serum samples are collected, one 5-30 minutes prior to the methylprednisolone infusion, the second one 30 minutes (±10 minutes) after the switch (shorter infusion) or the mimic switch (conventional infusion), and the third sample 30 minutes (±10 minutes) after completion of the infusion (at the end of ocrelizumab infusion for the conventional infusion or saline infusion for the shorter infusion). If a PK sample is missed on the first randomized visit, the 3 PK samples should be collected at the next blinded visit.

^f Vital signs will include the measurements of heart rate, systolic and diastolic blood pressures. Vital signs should be taken within 45 minutes prior to the premedication methylprednisolone (or an equivalent) infusion and administration of antihistaminics. In addition, vital signs should be obtained prior to the ocrelizumab/saline infusion, then every 15 minutes (± 5 minutes) for the first hour, followed by every 30 minutes (± 10 minutes) until 1 hour after the end of the infusion. Vital signs will be reported in the eCRF for all the blinded infusions from premedication till patient leaves the infusion site.

⁹ The period of evaluation of the IRRs will be 24 hours after the end of each blinded infusion. A structured telephone interview should be conducted by the site personnel on the following working day after the end of each blinded infusion, starting at week 24 to collect information on any possible IRRs or any other changes in the patient's health status, which may have occurred after the discharge.

* For patients who are already enrolled in the main study and only at the first infusion post randomization.

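### The SAP's vital-sign abnormality count ignores the pre-infusion reading, so patients already out of range can dilute this secondary safety comparison

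*SAP*

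**What the plan says.** SAP 4.5.4 lists three abnormality lines: "Systolic blood pressure <90mmHg or >140mmHg", "Diastolic blood pressure <50mmHg or >90mmHg" and "Pulse rate <60pm or >100bpm". Each puts a low and a high limit in one line, and none refers to the patient's starting value. The section then plans the table: "The number and percentage of patients with any vital signs abnormalities and with each abnormality described above will be presented". This is done for all patients and separately for patients with and without IRRs, by Randomized Dose and by Dose within it.

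The same section does set a reference reading. Its list of summarized time points opens with "Vital signs parameters prior to start of each ocrelizumab infusion (baseline", where the bracket closes. The only output that uses that reading is continuous: "The change from baseline will also be summarized (mean, SD, median, minimum and maximum". No shift table is planned, and the section does not say which time points feed the abnormality count.

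For adverse events the SAP takes an onset-based approach. In SAP 4.5.2.3, "Summaries of AEs will be generated summarizing the incidence of treatment-emergent AEs only".

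The readings exist. The substudy schedule of assessments (Protocol Appendix 10, its Appendix 1, vital-signs footnote) says that "Vital signs will be reported in the eCRF for all the blinded infusions from premedication till patient leaves the infusion site". The same footnote asks for one reading before premedication and another before the ocrelizumab infusion.

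**The concern.** The substudy asks whether the faster infusion is as safe as the conventional one. Hypotension and tachycardia are among the IRR symptoms named in Protocol 5.1.3.1, so a reader will look to the measured vital signs for changes brought on by the infusion. A patient who arrives with systolic pressure above 140 mmHg and stays there says nothing about infusion speed, but counts in the table like one who moved.

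Pre-existing abnormality is plausible here. The protocol's advice on considering withholding antihypertensive treatment before infusions (4.3.2.1, 4.4.1) implies that some patients take such treatment, and the exclusion criteria in 4.1.2 set no vital-sign limits. How many patients start out of range is not stated.

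Pooling low and high adds a second loss. If the table is built on the three listed lines, a patient who falls from above 140 to below 90 mmHg looks the same as one who stays above 140. A resting pulse below 60 likewise hides new tachycardia. At stake is how readable one descriptive table is, both between infusion groups and between patients with and without IRRs.

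**Working it through.** **No plan figure to reproduce.** The documents give no expected rate of vital-sign abnormality, before or after infusion. The rates below are assumptions and are shown over a range.

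**Step 1: are patients already out of range counted?** Two readings of SAP 4.5.4 are possible.
- If all time points feed the table, the pre-infusion value alone qualifies the patient.
- If only readings after infusion start count, a patient who starts and stays out of range still qualifies.

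Neither reading excludes them.

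**Step 2: formula.** Let b be the share out of range before infusion, q the share of those patients who are counted, and p1, p2 the new-onset rates in the conventional and shorter groups. Assume b and q are equal between groups.

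- Observed rate = b·q + (1-b)·p
- Observed risk difference (RD) = (1-b)·(p2 - p1), whatever q is
- Observed risk ratio (RR) = [b·q + (1-b)·p2] / [b·q + (1-b)·p1], which moves toward 1 when b·q > 0

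If all readings count, q = 1. Restricting to patients who start in range gives back p1 and p2, with n(1-b) per group.

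**Step 3: numbers with q = 1.** SAP 2.3 expects about 650 evaluable patients randomized 1:1, so n = 325 per group. Assume p1 = 10% and p2 = 15%. New-onset counting gives RD 5.0 points and RR 1.50 at every b. The planned count gives:

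| b | Conventional | Shorter | RD (points) | RR |
|---|---|---|---|---|
| 1% | 10.9% | 15.9% | 5.0 | 1.45 |
| 5% | 14.5% | 19.3% | 4.7 | 1.33 |
| 10% | 19.0% | 23.5% | 4.5 | 1.24 |
| 20% | 28.0% | 32.0% | 4.0 | 1.14 |
| 30% | 37.0% | 40.5% | 3.5 | 1.09 |
| 40% | 46.0% | 49.0% | 3.0 | 1.07 |

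Example at b = 20%: 0.20 + 0.80 × 0.10 = 0.28 and 0.20 + 0.80 × 0.15 = 0.32; RD = 0.04; RR = 0.32/0.28 = 1.14.

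**Step 4: effect relative to its standard error**, as a descriptive yardstick only (no test is planned). At b = 20%:
- planned count: 0.04 / √[(0.28×0.72 + 0.32×0.68)/325] = 1.11
- new onset, n = 0.8 × 325 = 260: 0.05 / √[(0.10×0.90 + 0.15×0.85)/260] = 1.73

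**Step 5: other inputs.** With assumed rates of 10% v 20% and 200 per group (the planned interim size):
- b = 20%: 28% v 36%, ratio 1.72 against 2.53 for new onset
- b = 40%: 46% v 52%, ratio 1.20 against 2.19

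Protocol 1.2 reports 291 and 289 patients randomized as of September 2019. At about 290 per group the same rates give 2.07 against 3.05 and 1.45 against 2.64. The absolute values depend on n; the relative loss does not.

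**Step 6: the milder reading.** If only later readings count and every patient who starts out of range returns to range (q = 0), b = 20% with 10% v 15% gives 8% v 12%. RD is still 4.0 points, but RR stays at 1.50. Step 3 is therefore the upper end for the risk ratio.

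**The case against.** A count of any abnormality against fixed limits is a legitimate descriptive output, and the laboratory abnormality summary in SAP 4.5.3.1 states no baseline condition either. The adverse-event parallel is loose, because treatment-emergent there is anchored to the first randomized dose, not to each infusion. These points stand, and they are why the planned count should be kept.

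Other outputs also cover part of the ground. Change from baseline includes the minimum and maximum, so the largest fall and rise at each time point are visible. There are box plots by Randomized Dose. IRR symptoms are tabulated by preferred term, during and after infusion (SAP 4.5.2.1), and a blinded investigator confirms the IRRs (SAP 3.1). New or worsened clinically significant vital-sign abnormalities go on the adverse event form (Protocol 4.5.4). None of these counts how many patients moved out of range on measured values.

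The size is assumed throughout. If low and high are tabulated separately and few patients start below 90 mmHg, dilution for hypotension is negligible. SAP 4.5.4 also does not say in words that pre-infusion readings count. A reader might infer that it does; the text supports only that such patients are not excluded.

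A tempting repair, counting only patients whose value was within both limits beforehand, would do harm. A patient going from 142 to 85 mmHg systolic would leave both numerator and denominator, although the planned table counts that patient.

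**Conclusion.** The point holds as a cheap improvement to a secondary, descriptive table. The planned count does not separate new from pre-existing abnormality, and the risk difference for new onset shrinks by (1-b). This assumes that pre-infusion status, and how often it persists, are balanced between the groups. Randomization supports that at the first randomized dose. IRR status is not randomized, so the same factor applies to that split only if b is similar in both subgroups.

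The direction is firm, but the size is not known: negligible at b of about 1%, material at 20% to 40%. The documents do not supply b.

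A reader might go further and infer that the substudy's safety comparison is undermined, or that infusion-induced hypotension would go unseen. The documents do not support that. The primary endpoint is the proportion of patients with IRRs at the first randomized infusion and does not use this table. SAP 4.5 describes the substudy as descriptive without formal inference, so no test loses power, and the other outputs would show much of any clinically relevant effect.

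**What to change.** Keep the planned count and add the following to SAP 4.5.4:

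- Per infusion, parameter and direction (low and high separately), give the number of patients not beyond that limit before infusion who go beyond it after infusion start. The denominator is the patients not beyond that limit before infusion. A low/normal/high shift table would serve equally. A fall from above 140 to below 90 mmHg is then still counted as a new low.
- For the row on any abnormality, count patients with at least one such new crossing among all infused patients with a pre-infusion reading.
- Show the pre-infusion out-of-range counts in separate rows.
- State which pre-infusion reading is baseline (before premedication or before ocrelizumab) and which time points feed the planned count.

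The cost is SAP wording, a few more table rows and minor programming on data already collected. One gap remains: worsening in the same direction in a patient already beyond a limit appears only in the planned count and the change-from-baseline summaries. Protocol Appendix 10, section 3.2, marks the substudy as complete, so the added table should be labelled supplementary.
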